## 8.3.5.2. Exposure During Breastfeeding

An exposure during breastfeeding occurs if:

- A female participant is found to be breastfeeding while receiving or after discontinuing study intervention.
- A female is found to be breastfeeding while being exposed or having been exposed to study intervention (ie, environmental exposure). An example of environmental exposure during breastfeeding is a female family member or healthcare provider who reports that she is breastfeeding after having been exposed to the study intervention by ingestion.

The investigator must report exposure during breastfeeding to Pfizer Safety within 24 hours of the investigator's awareness, irrespective of whether an SAE has occurred. The information must be reported using the CT SAE Report Form. When exposure during breastfeeding occurs in the setting of environmental exposure, the exposure information does not pertain to the participant enrolled in the study, so the information is not recorded on a CRF. However, a copy of the completed CT SAE Report Form is maintained in the investigator site file.

An exposure during breastfeeding report is not created when a Pfizer drug specifically approved for use in breastfeeding women (eg, vitamins) is administered in accord with authorized use. However, if the infant experiences an SAE associated with such a drug, the SAE is reported together with the exposure during breastfeeding.

## 8.3.5.3. Occupational Exposure

The investigator must report any instance of occupational exposure to Pfizer Safety within 24 hours of the investigator's awareness using the CT SAE Report Form regardless of whether there is an associated SAE. Since the information about the occupational exposure does not pertain to a participant enrolled in the study, the information is not recorded on a CRF; however, a copy of the completed CT SAE Report Form must be maintained in the investigator site file.

#### 8.3.6. Cardiovascular and Death Events

Not applicable.

## 8.3.7. Disease-Related Events and/or Disease-Related Outcomes Not Qualifying as AEs or SAEs

Not Applicable.

## 8.3.8. Adverse Events of Special Interest

Not Applicable.

#### 8.3.8.1. Lack of Efficacy

This section is not applicable because efficacy is not expected in the study population.

## 8.3.9. Medical Device Deficiencies

Not Applicable.

#### 8.3.10. Medication Errors

Medication errors may result from the administration or consumption of the study intervention by the wrong participant, or at the wrong time, or at the wrong dosage strength.

Exposures to the study intervention under study may occur in clinical trial settings, such as medication errors.

Safety Event	Recorded on the CRF	Reported on the CT SAE Report Form to Pfizer Safety Within 24 Hours of Awareness
Medication errors	All (regardless of whether associated with an AE)	Only if associated with an SAE

Medication errors include:

- Medication errors involving participant exposure to the study intervention;
- Potential medication errors or uses outside of what is foreseen in the protocol that do or do not involve the study participant.

Such medication errors occurring to a study participant are to be captured on the medication error page of the CRF, which is a specific version of the AE page.

In the event of a medication dosing error, the sponsor should be notified within 24 hours.

Whether or not the medication error is accompanied by an AE, as determined by the investigator, the medication error is recorded on the medication error page of the CRF and, if applicable, any associated AE(s), serious and nonserious, are recorded on the AE page of the CRF.

Medication errors should be reported to Pfizer Safety within 24 hours on a CT SAE Report Form **only when associated with an SAE.** 

#### 8.4. Pharmacokinetics

Blood samples of approximately 4 mL, to provide approximately 1.5 mL plasma, will be collected for measurement of plasma concentrations of prazosin as specified in the SoA. Instructions for the collection and handling of biological samples will be provided in the laboratory manual or by the sponsor. The actual date and time (24-hour clock time) of each sample will be recorded.

The actual times may change, but the number of samples will remain the same. All efforts will be made to obtain the samples at the exact nominal time relative to dosing. Collection of samples up to and including 10 hours after dose administration that are obtained within 10% of the nominal time (eg, within 6 minutes of a 60-minute sample) relative to dosing will not be captured as a protocol deviation, as long as the exact time of the collection is noted on the source document and data collection tool (eg, CRF/DCT). Collection of samples more than 10 hours after dose administration that are obtained ≤1 hour away from the nominal time relative to dosing will not be captured as a protocol deviation, as long as the exact time of the collection is noted on the source document and data collection tool (eg, CRF/DCT).

Genetic analyses will not be performed on these plasma samples. Participant confidentiality will be maintained.

Samples collected for measurement of plasma concentrations of prazosin will be analyzed using a validated analytical method in compliance with applicable standard operating procedures (SOPs).

The PK samples must be processed and shipped as indicated in the instructions provided to the investigator site to maintain sample integrity. Any deviations from the PK sample handling procedure (eg, sample collection and processing steps, interim storage or shipping conditions), including any actions taken, must be documented and reported to the sponsor. On a case-by-case basis, the sponsor may make a determination as to whether sample integrity has been compromised.

#### 8.5. Genetics

## 8.5.1. Specified Genetics

Genetics (specified analyses) are not evaluated in this study.

## 8.5.2. Retained Research Samples for Genetics

A 4 mL blood sample optimized for DNA isolation Prep D1 will be collected according to the SoA, as local regulations and IRBs/ECs allow.

Retained Research Samples may be used for research related to the study intervention(s). Genes and other analytes (eg, proteins, RNA, nondrug metabolites) may be studied using the banked samples.

See Appendix 5 for information regarding genetic research. Details on processes for collection and shipment of these samples can be found in Lab Manual.

#### 8.6. Biomarkers

Biomarkers are not evaluated in this study.

#### 8.7. Immunogenicity Assessments

Immunogenicity assessments are not included in this study.

#### 8.8. Health Economics

Health economics/medical resource utilization and health economics parameters are not evaluated in this study.

#### 9. STATISTICAL CONSIDERATIONS

Detailed methodology for summary and statistical analyses of the data collected in this study is outlined here and further detailed in a SAP, which will be maintained by the sponsor. The SAP may modify what is outlined in the protocol where appropriate; however, any major modifications of the primary endpoint definitions or their analyses will also be reflected in a protocol amendment.

#### 9.1. Statistical Hypotheses

The alternative hypothesis of bioequivalence (H1:  $\theta_L <= \mu_T - \mu_R <= \theta_U$ ), and the null hypothesis of inequivalence (Ho:  $\mu_T - \mu_R < \theta_L$  or  $\mu_T - \mu_R > \theta_U$ ) can be expressed as the following 2 separate one-sided hypotheses:

HoA: 
$$\mu_T - \mu_R < \theta_L$$
  
H1A:  $\theta_L <= \mu_T - \mu_R$ 

HoB: 
$$\mu_T$$
 -  $\mu_R$  > $\theta_U$   
H1B:  $\mu_T$  -  $\mu_R$  <= $\theta_U$ 

where  $\mu T$  and  $\mu R$  represent the average bioavailability on a log scale for the Test and Reference products respectively and  $[\theta L, \theta U]$  defines the bioequivalence range.

Bioequivalence of the Test treatment to Reference treatment will be concluded if the 90% confidence intervals for the ratios of adjusted geometric means for prazosin AUClast and  $C_{max}$  fall entirely within the acceptance region of (80%, 125%).

## 9.2. Analysis Sets

For purposes of analysis, the following analysis sets are defined:

Participant Analysis	Description
Set	
Enrolled/Randomly assigned to study intervention	Participants will be randomized into the study provided they have satisfied all participant eligibility criteria.
PK concentration population	All participants randomized and treated who have at least 1 concentration in at least 1 treatment period.
Safety	All participants randomly assigned to study intervention and who take at least 1 dose of investigational product.

#### 9.3. Statistical Analyses

The SAP will be developed and finalized before any analyses are performed and will describe the analyses and procedures for accounting for missing, unused, and spurious data. This section is a summary of the planned statistical analyses of the primary and secondary endpoints.

#### 9.3.1. Primary Endpoint(s)

#### 9.3.1.1. Determination of Pharmacokinetic Parameters

Pharmacokinetic parameters will be derived from the concentration-time profiles as shown in Table 5.

Table 5. PK Parameters

Parameter	Definition	Method of Determination
AUC last	Area under the plasma concentration-time curve from time zero to the time of the last quantifiable concentration (C last ).	Linear-log trapezoidal method.
AUC inf	Area under the plasma concentration-time curve from time zero extrapolated to infinite time.	AUC last + (C last */k el ), where C last * is the predicted plasma concentration at the last quantifiable time point estimated from the log-linear regression analysis.
C max	Maximum plasma concentration.	Observed directly from data.
$T_{max}$	Time to first occurrence of C max .	Observed directly from data as time of first occurrence.
$t_{1/2}$	Terminal elimination half-life.	Ln(2)/k el , where k el is the terminal phase rate constant calculated by a linear regression of the log linear concentration-time curve. Only those data points judged to describe the terminal log-linear decline will be used in the regression.

Actual PK sampling times will be used in the derivation of PK parameters.

#### 9.3.2. Statistical Analysis of Pharmacokinetic Parameter

Pharmacokinetic and statistical analysis will be performed for prazosin. Data from 2 Cohorts will be analyzed separately.

The PK parameters AUClast, AUCinf, Cmax, Tmax, and t½ will be summarized descriptively by analyte and treatment. For AUClast, AUCinf and Cmax parameters, individual data and geometric mean will be plotted with box plots by analyte and treatment for each parameter. Plasma concentration data will be listed and summarized descriptively by analyte, PK sampling time and treatment. Individual participant and summary profiles (mean and median) of the plasma concentration-time data will be plotted against analyte by treatment. Mean and median profiles will be presented on both linear-linear and log-linear scales. For summary statistic and summary (mean and median) plots by sampling time, the nominal PK sampling time will be used.

#### Cohort 1:

Natural log transformed PK parameters ( $AUC_{inf}$ ,  $AUC_{last}$ , and  $C_{max}$ ) will be analyzed using a mixed effect model with sequence, period and treatment as fixed effects and participant within sequence as a random effect. Estimates of the adjusted mean differences (Test – Reference) and the corresponding 90% confidence intervals will be obtained from the model. The adjusted mean differences and the 90% confidence intervals for the differences

will be exponentiated to provide estimates of the ratio of adjusted geometric means (Test/Reference) and the 90% confidence intervals for the ratios.

For primary objective, bioequivalence of the Test treatments (Treatment B and Treatment C) relative to Reference treatment (Treatment A) will be concluded if the 90% confidence intervals for the ratio of adjusted geometric means of Test treatments (Treatment B and Treatment C) relative to Reference treatment (Treatment A) for AUCinf (if data permit), AUClast and Cmax fall wholly within (80%, 125%).

#### Cohort 2:

Natural log transformed PK parameters (AUCinf, AUClast, and Cmax) will be analyzed using a mixed effect model with sequence, period and treatment as fixed effects and participant within sequence as a random effect. Estimates of the adjusted mean differences (Test – Reference) and the corresponding 90% confidence intervals will be obtained from the model. The adjusted mean differences and the 90% confidence intervals for the differences will be exponentiated to provide estimates of the ratio of adjusted geometric means (Test/Reference) and the 90% confidence intervals for the ratios.

For primary objective, bioequivalence of the Test treatment (Treatment E) relative to Reference treatment (Treatment D) will be concluded if the 90% confidence intervals (CI) for the ratio of adjusted geometric means of Treatment E (5 mg capsule, Ascoli) relative to Treatment D (5 mg capsule, Barceloneta) for AUCinf (if data permit), AUClast and Cmax, fall wholly within (80%, 125%).

#### 9.3.3. Safety analyses

All safety analyses will be performed on the safety population.

The safety data will be described and summarized in accordance with the Sponsor's Data Standards.

AEs, ECGs, BP, pulse rate, and safety laboratory data will be reviewed and summarized on an ongoing basis during the study to evaluate the safety of participants. Any clinical laboratory, ECG, BP, and pulse rate abnormalities of potential clinical concern will be described. Medical history and physical examination and neurological examination information, as applicable, collected during the course of the study will be considered source data and will not be required to be reported, unless otherwise noted. However, any untoward findings identified on physical and/or neurological examinations conducted during the active collection period will be captured as AEs, if those findings meet the definition of an AE. Data collected at screening that are used for inclusion/exclusion criteria, such as laboratory data, ECGs, and vital signs, will be considered source data, and will not be required to be reported, unless otherwise noted. Demographic data collected at screening will be reported.

## 9.3.4. Other Analyse(s)

There are no other analyses included in this study.

#### 9.4. Interim Analyses

No formal interim analysis will be conducted for this study. As this is an open-label study, the sponsor may conduct unblinded reviews of the data during the course of the study for the purpose of safety assessment, facilitating PK/PD modeling, and/or supporting clinical development.

#### 9.5. Sample Size Determination

#### Cohort 1:

A sample size of 30 participants will provide at least 95% power that the 90% confidence interval for the ratio of Test to Reference treatment for both AUC $_{last}$  and  $C_{max}$  of prazosin, individually will lie within the acceptance region of (80%, 125%). Consequently, this study will have approximately 90% overall power to demonstrate bioequivalence of the Test treatment to the Reference treatment [ie, equivalence for both AUC and  $C_{max}$ ], where overall power for the study is based on the product of the individual powers of the parameters of interest. This estimate is based on the assumption that the true ratio between Test and Reference treatments for both AUC $_{last}$  and  $C_{max}$  is 0.95 and also assumes within-participant standard deviations of 0.198 for both  $log_e$  AUC $_{last}$  and  $log_e$   $C_{max}$ , as obtained from the literature.

To allow for dropouts, 36 participants will be enrolled in order to have 30 PK evaluable participants. Dropouts for non-safety reasons may be replaced at the discretion of the sponsor and investigator.

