2.2. Study Objectives

Primary:

- To demonstrate bioequivalence between prazosin HCL 1 and 2 mg capsules manufactured at the proposed site (Ascoli) versus prazosin HCl 2 mg capsules manufactured at the current site (Barceloneta) under fasting conditions in healthy adult participants.
- To demonstrate bioequivalence between prazosin HCl 5 mg capsules manufactured at the proposed site (Ascoli) versus prazosin HCl 5 mg capsules manufactured at the current site (Barceloneta) under fasting conditions in healthy adult participants.

Secondary:

• To evaluate the safety and tolerability of prazosin HCl capsules.

	Page 6 of 17	
	PFIZER CONFIDENTIAL	

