4. HYPOTHESES AND DECISION RULES

4.1. Statistical Hypotheses

4.1.1. Bioequivalence Hypotheses

The alternative hypothesis of bioequivalence ($H_1: \theta_L \leq = \mu_T - \mu_R \leq = \theta_U$), and the null hypothesis of inequivalence ($H_0: \mu_T - \mu_R \leq \theta_L$ or $\mu_T - \mu_R \geq \theta_U$) can be expressed as the following two separate one-sided hypotheses:

HoA: $\mu_T - \mu_R < \theta_L$

*H*₁*A*: $\mu_T - \mu_R >= \theta_L$

Hob: $\mu_T - \mu_R > \theta_U$

*H*_{1B}: $\mu_T - \mu_R <= \theta_U$

where μ_T and μ_R represent the average bioavailability on a log scale for the Test and *Reference products, respectively and* $[\theta_L, \theta_U]$ *defines the bioequivalence range.*

Bioequivalence of the Test treatment to Reference treatment will be concluded if the 90% confidence intervals for the ratios of adjusted geometric means for prazosin AUC_{last} and C_{max} fall entirely within the acceptance region of (80%, 125%).

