8.2. Statistical Analyses

Pharmacokinetic and statistical analysis will be performed for prazosin. Data from the 2 Cohorts will be analyzed separately.

Cohort 1:

Natural log transformed PK parameters (AUC_{inf} (if data permit), AUC_{last} , and C_{max}) will be analyzed using a mixed effect model with sequence, period and treatment as fixed effects and participant within sequence as a random effect. Estimates of the adjusted mean differences (Test-Reference) and the corresponding 90% confidence intervals will be obtained from the model. The adjusted mean differences and the 90% confidence intervals for the differences will be exponentiated to provide estimates of the ratio of adjusted geometric means (Test/Reference) and the 90% confidence intervals for the ratios.

Page 11 of 17

For primary objective, bioequivalence of the Test treatments (Treatment B and Treatment C) relative to Reference treatment (Treatment A) will be concluded if the 90% confidence intervals for the ratio of adjusted geometric means of Test treatments (Treatment B and Treatment C) relative to Reference treatment (Treatment A) for AUC_{last} and C_{max} fall wholly within (80%, 125%).

Cohort 2:

Natural log transformed PK parameters (AUC_{inf} (if data permit), AUC_{last} , and C_{max}) will be analyzed using a mixed effect model with sequence, period and treatment as fixed effects and participant within sequence as a random effect. Estimates of the adjusted mean differences (Test-Reference) and the corresponding 90% confidence intervals will be obtained from the model. The adjusted mean differences and the 90% confidence intervals for the differences will be exponentiated to provide estimates of the ratio of adjusted geometric means (Test/Reference) and the 90% confidence intervals for the ratios.

For primary objective, bioequivalence of the Test treatment (Treatment E) relative to Reference treatment (Treatment D) will be concluded if the 90% confidence intervals (CI) for the ratio of adjusted geometric means of Treatment E (5 mg capsule, Ascoli) relative to Treatment D (5 mg capsule, Barceloneta) for AUC_{last} and C_{max} , fall wholly within (80%, 125%).

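### Protocol 9.5 calls about 90% the overall study power for Cohort 1, but that figure covers one Test-Reference comparison; if Treatments B and C must both pass, it is about 84% on the plan's own convention

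*Protocol*

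**What the plan says.** Protocol 9.5, Cohort 1, assumes a true ratio of 0.95 and a within-participant SD of 0.198 for log AUClast and log Cmax. It claims at least 95% power for each parameter at 30 participants, then concludes: "Consequently, this study will have approximately 90% overall power to demonstrate bioequivalence of the Test treatment to the Reference treatment". A bracket explains that this means equivalence on both AUC and Cmax, and the sentence adds that "overall power for the study is based on the product of the individual powers of the parameters of interest". On numbers it says that "36 participants will be enrolled in order to have 30 PK evaluable participants" and that "Dropouts for non-safety reasons may be replaced at the discretion of the sponsor and investigator". The Cohort 2 paragraph uses the same overall-power sentence, with 32 evaluable participants and a single Test product.

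Cohort 1 compares two Test products (B, the 2 mg capsule; C, two 1 mg capsules) with one Reference (A). Its objective puts them in one sentence: "To demonstrate bioequivalence between prazosin HCL 1 and 2 mg capsules manufactured at the proposed site (Ascoli) versus prazosin HCl 2 mg capsules" (SAP 2.2; Protocol 3 is the same in substance). The Cohort 1 decision sentence in Protocol 9.3.2 also names both: "bioequivalence of the Test treatments (Treatment B and Treatment C) relative to Reference treatment (Treatment A) will be concluded if the 90% confidence intervals" meet the limits. SAP 8.2 repeats it.

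Other text is in the singular. SAP 4.1.1 reads: "Bioequivalence of the Test treatment to Reference treatment will be concluded if the 90% confidence intervals for the ratios of adjusted geometric means" for AUClast and Cmax lie within the limits, and Protocol 9.1 agrees. SAP 4.2 and 4.2.1 require both parameters but do not mention two products. The Cohort 1 code in SAP Appendix 1 produces separate B versus A and C versus A intervals.

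**The concern.** A power described as overall for the study should match the decision that the study is meant to reach. In Cohort 2 it does, for that cohort, because there is one Test product. In Cohort 1 the same wording is carried over although there are two, and nothing in 9.5 counts the second comparison.

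Two things follow. If the Cohort 1 objective is met only when both products pass, the chance of missing it at 30 evaluable participants is about 16% on the plan's convention, not the 10% or so that a reader takes from 9.5. And if one product passes while the other fails, the documents do not say whether bioequivalence may be concluded for the one that passed. That is better settled before data are seen, since the study is open-label and allows unblinded data reviews (Protocol 9.4, SAP 3).

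**Working it through.** **Inputs.** Ratio 0.95, SD 0.198, 30 evaluable, limits 80% to 125% (Protocol 9.5); two one-sided tests at 0.05 (SAP 4.2.1); three treatments in three periods with shared Reference A (Protocol 4.1); mixed model with Kenward-Roger degrees of freedom (SAP 8.1), which for complete balanced data is taken as 2n − 4 = 56.

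**Step 1: reproduce the plan's figure.** SE = 0.198 × √(2/30) = 0.0511. The true difference is d = ln 0.95 = −0.0513 and the limits are ±0.2231.

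Normal approximation: lower side (0.2231 − 0.0513)/0.0511 − 1.645 = 1.717, probability 0.957; the upper side is essentially 1. Power is about 0.957.

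Exact: average Φ[(U − d)/SE − t√V] − Φ[(L − d)/SE + t√V] over V ~ χ²(df)/df. With df = 56 this gives 0.953 per parameter, and 0.953² = 0.908 for AUClast and Cmax together. With df = n − 2 = 28 it gives 0.949 and 0.900. So 95% and 90% reproduce for one Test-Reference comparison.

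**Step 2: add the second product.** B − A and C − A share the mean of A. Their covariance is σ²/n and each variance is 2σ²/n, so their correlation is 0.5; they also share the residual variance estimate. For one parameter, writing lo and hi for the standardised limits in Step 1, the joint power is the average of [Φ(√2·hi − u) − Φ(√2·lo − u)]² over u ~ N(0,1) and V.

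- 30 evaluable, df 56: 0.917 per parameter; squared over the two parameters, **0.842**.
- 30 evaluable, df 28: 0.911; squared, 0.830.
- 34 evaluable: 0.898. 35 evaluable: 0.909.
- 36 evaluable, df 68: 0.959; squared, **0.919**.

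Multiplying four powers as if the comparisons were independent (0.953⁴ = 0.825) ignores the shared Reference and is too low.

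**Step 3: relax independence of AUClast and Cmax.** The documents give no correlation, so the values below are assumptions. Joint power for B and C on both parameters, by simulation (1,000,000 trials per cell):

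| Assumed correlation | 30 evaluable | 36 evaluable |
|---|---|---|
| 0 (plan's product convention) | 0.842 | 0.919 |
| 0.5 | 0.858 | 0.926 |
| 0.7 | 0.869 | 0.932 |
| 0.9 | 0.889 | 0.942 |
| 0.95 | 0.897 | 0.947 |

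A participant-level simulation of the six-sequence design (40,000 trials) agreed: 0.843 at 30 and 0.920 at 36 with correlation 0.

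**Not counted.** The Protocol 9.3.2 rule adds AUCinf if data permit; the power statement in 9.5 and the SAP 8.2 rule do not. Including it could only leave these figures equal or lower them.

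**The case against.** The best defence is that 9.5 defines its own term. The sentence speaks of one Test treatment, its bracket limits equivalence to AUC and Cmax, and the product is taken over parameters. Read closely, overall means across parameters for one product, and for that 90% is right. The two sample sizes fit this reading: a three-period analysis reaches 95.3% at 30, whereas a two-period analysis gives 94.9% at 30 and 96.0% at 32. The documents do not state the degrees of freedom, so this is an inference, but it suggests that each cohort was sized per comparison for its own design.

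A per-product conclusion is also open on the text: the general hypotheses and rules are singular, and the code yields two separate intervals. And 84% is the bottom of the range over assumed non-negative correlations. AUClast and Cmax come from the same concentration curve, and at a correlation of 0.9 joint power is about 89%, which fits a claim of approximately 90%.

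All of this stands, and it limits the point. What remains is that the same sentence attaches the figure to the study, that the Cohort 1 objective and decision sentences name both products, and that no text says whether B and C are judged separately.

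A reader might infer that the power calculation is wrong or that Cohort 1 is underpowered. The documents do not support that: the calculation reproduces, and the shortfall exists only if both products must pass. With all 36 evaluable, joint power is about 92% or more. Non-safety dropouts may be replaced, and participants with partial data stay in the parameter set and the mixed model (SAP 5.2.2, 8.1).

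**Conclusion.** The point holds as one of labelling and scope, at low severity. The stated 90% is the power for one Test-Reference comparison on AUClast and Cmax (0.908 at 30 evaluable). If B and C must both pass, power at 30 evaluable is about 84% on the plan's product convention, about 86% to 90% at assumed correlations of 0.5 to 0.95, and about 92% at 36 evaluable on the product convention. If each product is concluded separately, 90% stands per comparison and only the label needs changing.

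These figures rest on the plan's ratio and SD holding for both products and both parameters, on complete data with 2n − 4 degrees of freedom, and on leaving AUCinf out. It would be going too far to present 84% as the power of Cohort 1 without condition: the plan has not said that both must pass, and the figure treats AUClast and Cmax as independent.

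**What to change.** - Protocol 9.5, Cohort 1: replace the description of the figure as overall study power with *approximately 90% power per Test-Reference comparison (AUClast and Cmax)*.
- Protocol 9.3.2 and SAP 8.2, Cohort 1: state whether bioequivalence is concluded separately for Treatment B and Treatment C, or only if both pass.
- Only if both must pass, add to 9.5: *Power for Treatments B and C both to meet the criteria on AUClast and Cmax is about 84% with 30 evaluable participants and about 92% with 36, taking the product over the two parameters and not counting AUCinf; it is higher if the parameters are positively correlated.*

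The cost is a few sentences. The one downside is a less favourable stated figure if both products must pass. Enrolment, analysis and type I error do not change.
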